Next, we will examine maternal experience of violence or homicide during the index pregnancy and during the first 24 months after the index birth using a combination of death records and Medicaid and hospital discharge data. This is defined as any record matching a code listed in

---

ii In our study protocol (McConnell et al 2020) we indicated that we planned to derive neonatal morbidity from discharge records. However, in order to make our analyses parallel with other analyses looking at neonatal morbidity (Han et al 2020) and because of concerns about the ability to translate these concepts directly into claims data (Ford et al 2007), we plan to rely instead on birth certificate data.

Table 1.2. As above, experience of violence was originally specified over 24 months, but we will explore analysis of this outcome during the index pregnancy because of the negative associations between exposure to maternal violence and birth outcomes. Our current definitions of substance abuse and maternal experience of violence are limited to the codes defined here; however, we will explore incorporating broader indicators of challenges with substance abuse derived from pharmacy claims, child claims, and criminal justice records. We will update these outcome specifications prior to any analysis of comparisons across treatment and control groups for these outcomes.

We will also examine use of social services during pregnancy and during the first 24 months after delivery. During pregnancy, we will examine any receipt of WIC benefits (derived from the birth certificate) and any receipt of Supplemental Nutrition Assistance Program (SNAP) benefits (from South Carolina Department of Social Services data). During the first 24 months after delivery, we will examine total months of receiving SNAP benefits and Temporary Assistance for Needy Families (TANF) benefits, as well as a measure of benefit churn, defined as receiving SNAP or TANF benefits at any time during a given year and having experienced at least one break in participation of four months or less that started and/or ended during the year.

Table 1.1. Codes for composite outcomes related to neonatal abstinence disorder and maternal drug/substance abuse

Code Description	ICD-10 Code(s)
Neonatal abstinence disorder	P96.1, P04*
Opioids	F11.*
Tobacco	F17.2*, O99.33*, Z72.0
Alcohol	V11.3*, F10.*
Sedative	F13.*
Cocaine	F14.*
Amphetamines	F15.*
Cannabis	F12.*

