Source: Jarlenski et al. 2020^16

Table 1.2. Codes for maternal experience of violence

Code Description	ICD-10 Code(s)
Adult neglect	T74.01; T76.01
Adult physical abuse	T74.11; T76.11
Adult sexual abuse	T74.21; T76.21
Adult psychological abuse	T74.31; T76.31
Unspecified adult maltreatment	T74.91; T76.91

Husband, perpetrator of maltreatment	Y0701
Assault by unarmed brawl	Y040
Observation after rape	Z0441
Assault by other bodily force	Y048
Unspecified perpetrator of maltreatment	Y079
Other family member perpetrator of maltreatment	Y07499
Encounter for mental health services for victim of spousal or partner abuse	Z691x
Encounter for mental health services for victim or perpetrator of other abuse	Z698x
Encounter for observation following alleged adult physical abuse	Z0471

Sources: Crosswalk of ICD-9 to ICD-10 codes from Davidov et al. 2017 and Schafer et al. 2008.

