**Table 8. Mental health outcomes**

	Primary/secondary	Desired direction (increase or decrease)

Any outpatient treatment or diagnosis (preg-60d)	secondary	increase
Antidepressant prescription (preg-60d)	secondary	increase
Outpatient mental health visit (preg-60d)	secondary	increase
Treatment follow up (within 120d)	secondary	increase
Mental health related emergency/inpatient visit (preg-1y)	secondary	decrease
Number of mental health related emergency/inpatient visits (preg-1y)	secondary	decrease
Neonatal abstinence disorder or maternal drug/substance use (2y)	secondary	decrease
Maternal experience of violence or homicide (2y)	secondary	decrease

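### The code list for maternal violence or homicide has no homicide or weapon-assault row, labels its maltreatment rows adult although mothers enrol from age 15, and counts perpetrator encounters

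*SAP*

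**What the plan says.** In SAP Addendum 1, section 1.2.1 Secondary Outcomes, the authors write that "we will examine maternal experience of violence or homicide during the index pregnancy and during the first 24 months after the index birth". The outcome is built "using a combination of death records and Medicaid and hospital discharge data. This is defined as any record matching a code listed in" Table 1.2. The section then says: "Our current definitions of substance abuse and maternal experience of violence are limited to the codes defined here". It goes on to say that "we will explore incorporating broader indicators of challenges with substance abuse derived from pharmacy claims, child claims, and criminal justice records", and it commits to updating the specifications before treatment and control are compared on these outcomes.

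Table 1.2 is titled for violence only and credits a crosswalk from two published studies. It has 14 rows, among them "Adult physical abuse", "Assault by unarmed brawl" and "Encounter for mental health services for victim or perpetrator of other abuse".

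Protocol section 4.4 admits applicants aged 15 to 55. Addendum 4, dated February 2025, keeps the 24-month version as a secondary outcome in Table 8, one of eight items there, and gives no further codes.

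**The concern.** The case rule is a closed any-match rule, so the outcome is whatever the rows of Table 1.2 can catch. Read against the outcome's name and the eligible population, the table falls short in three ways.

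- **Homicide and weapons.** The outcome names homicide and draws on death records, but no row describes either a homicide or an armed assault.
- **Minors.** The maltreatment rows are written for adults, while the trial enrols girls of 15 to 17. They also fall in the primary subgroup, which includes women under 19 (SAP 1.6).
- **Perpetrators.** One row covers victims and perpetrators together, so a mother seen as a perpetrator would be a case.

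The main risk is to validity. A null result reported for violence or homicide would claim coverage of the most severe events that the rule does not give. The same variable also enters the Addendum 4 index built from Table 8.

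**Working it through.** The documents give no event rate, sample size or power for this outcome, so the main check is a row-by-row reading.

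**Step 1. Sort the 14 rows of Table 1.2 by their own labels.**

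| Group | Rows | Count |
|---|---|---|
| Labelled adult | five T74/T76 maltreatment rows; Z0471 | 6 |
| Assault | Y040 (unarmed brawl); Y048 (other bodily force) | 2 |
| Neither adult-labelled nor assault | Z0441 (rape observation); Y0701, Y079, Y07499 (perpetrator identity); Z691x; Z698x | 6 |
| Homicide, or assault with a weapon | none | 0 |

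6 + 2 + 6 = 14.

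**Step 2. Apply the any-match rule to particular events.**

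- *Weapon homicide on a death record:* no row describes it, so it does not match.
- *Unarmed homicide:* could match Y040 or Y048.
- *Non-fatal weapon assault:* counts only if the record also carries a listed code, such as a perpetrator-identity or maltreatment row.
- *Maltreatment of a mother under 18:* on the labels, the six adult rows do not fit; the other eight could.
- *Mother seen as a perpetrator under Z698x:* counted as a case.

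**Step 3. Size the under-18 group.** Addendum 4, Table 1 defines under 18 as an expected delivery date before the 18th birthday, and Table 3 gives the counts.

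- Home visiting: 225/3,295 = 6.83% (stated 6.8%).
- Usual care: 117/1,637 = 7.15% (stated 7.1%).
- Pooled: (225 + 117)/(3,295 + 1,637) = 342/4,932 = 6.9%.

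This is a floor for mothers who were minors at some point in the index pregnancy, because it leaves out those who turned 18 before the due date. It is not the share affected throughout the 24-month window: a mother aged 16 or 17 at delivery reaches 18 by the end of it, and the adult rows then fit.

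**Step 4. Illustrate the effect of miscounting, on assumed values only.** Let the true control prevalence be p, with a 20% relative reduction, sensitivity s and false-positive rate f, the same in both arms. The observed risks are

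- control: s·p + f·(1 − p)
- treated: s·0.8p + f·(1 − 0.8p)

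For p = 5%, s = 0.8 and f = 0.005:

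- control: 0.8 × 0.05 + 0.005 × 0.95 = 0.0448
- treated: 0.8 × 0.04 + 0.005 × 0.96 = 0.0368
- risk ratio: 0.82 instead of 0.80

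Power with 1,637 and 3,295 mothers (two-sided 5% test of two proportions, normal approximation):

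| Assumed control prevalence | Perfect coding | s = 0.9, f = 0.002 | s = 0.8, f = 0.005 |
|---|---|---|---|
| 3% | 0.25 | 0.21 | 0.18 |
| 5% | 0.37 | 0.33 | 0.28 |
| 8% | 0.55 | 0.49 | 0.43 |

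Over these prevalences the observed risk ratio is 0.805 to 0.814 in the middle scenario and 0.815 to 0.835 in the last. None of the assumed values comes from the documents.

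**The case against.** The strongest reply is that the list is declared provisional. The SAP calls the definitions current and promises to update them before any arm comparison, so the gap can still be closed on the plan's own terms. That stands as to timing. It does not supply content: the only broadening described concerns substance abuse, and Addendum 4 keeps the outcome without new codes. Addendum 4's silence is weak evidence by itself, since it draws on manuscripts that are not among these documents.

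A second reply is that the list applies equally to both arms, so the harm is mostly under-counting and modest dilution, as step 4 suggests. That is fair for power. Equal codes need not mean equal detection, because Protocol 7.4 says the program's nurses are trained to screen for domestic violence and refer. A difference in detection is a reasonable inference, but the documents do not show one.

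A reader might also infer more than the documents support:

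- *That the list holds only adult maltreatment and unarmed assault.* Six of the 14 rows are neither, and they could catch some violence against minors or with a weapon.
- *That no homicide or weapon assault can ever count.* An unarmed homicide may match an assault row, and a weapon assault may carry another listed code.
- *That Z691x also scores perpetrators.* Its label names victims of spousal or partner abuse only.
- *That the perpetrator-identity rows score perpetrators.* They describe who harmed the patient.

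**Conclusion.** The point holds as a defect in outcome definition. Under the written rule, weapon homicide is not countable, weapon assault is countable only indirectly, the adult-labelled rows do not fit mothers under 18, and Z698x admits perpetrators. The homicide point is the firmest, since it needs only the outcome's name, the any-match rule and the table. The point about minors assumes that rows labelled adult are not used for a patient under 18; the labels suggest this, but the documents do not state the coding convention.

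The one size available is 342/4,932 = 6.9% under 18 at expected delivery, and it bears mainly on the pregnancy-window version. A reader might take it as the share lost from the 24-month result. The documents do not support that, because mothers aged 16 or 17 at delivery reach 18 within that window and no finer age split is given. Without event rates, the number of cases missed or wrongly counted cannot be estimated. This is a secondary outcome, and the change is worth making because it is cheap and the result should measure what its name says.

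**What to change.** Within the update that section 1.2.1 already promises, before the arms are compared, and for both the pregnancy and 24-month versions:

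1. State that homicide is identified from the cause of death on the mother's death record.
2. Add codes for assault with a weapon.
3. Add the maltreatment codes that apply to mothers under 18 at the encounter.
4. Restrict Z698x to victim encounters. Leave Z691x as it is.
5. Keep the present crosswalk list as a sensitivity definition.

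The documents do not say whether the arms have already been compared on this outcome. If they have, report the revised definition as a labelled sensitivity analysis.

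The cost is a code-list revision on record types the plan already uses for this outcome. The drawback is a departure from the cited crosswalk, which item 5 covers.

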### Antenatal Care Utilization & Quality

Analyses of outcomes related to antenatal care utilization and quality is planned as a stand-alone analysis. We will examine three groups of outcomes related to antenatal care utilization and quality: utilization of health care services during pregnancy, guideline-recommended antenatal care, and indicators related to antenatal health. We list the outcomes that fall under each area, and their associated data sources, below. We also include the CPT/HCPCS, NDC (National Drug Code) and ICD-10 codes used to identify the outcomes that use Medicaid claims or hospital discharge data in Table 1.3.

The primary sample for this analysis will be mothers with an index birth. We will use vital records, hospital discharge, and Medicaid claims data for the analyses. Mothers who do not match to one of these data sources will not be included in the sample for the corresponding outcomes (e.g., mothers who do not match to Medicaid claims will not be included in the analyses of guideline-recommended antenatal care).

### Utilization of health care services during pregnancy

- Adequacy of Prenatal Care Utilization Index (APNCU) [vital records data]
- Number of emergency department visits during pregnancy [all-payer hospital discharge data]
  - To better understand the effect of NFP on emergency department utilization, we may also examine treatment vs. control differences in emergency department use by trimester of the emergency department visit and by the enrollee's overall adequacy of prenatal care (APNCU).
- Number of ultrasounds during pregnancy [Medicaid claims data]

- Consultation with maternal fetal medicine specialist [all-payer hospital discharge data]
- Dental visit during pregnancy [Medicaid claims data]

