#### Antenatal health

- Smoking cessation during pregnancy [vital records data]
  - We will consider an enrollee to have ceased smoking during pregnancy if their vital record indicates that they smoked pre-pregnancy and that they did not smoke during pregnancy.
- Recommended gestational weight gain [vital records data]
  - Gestational weight gain will be classified as “recommended” if it is within the guidelines published by the National Academy of Medicine (formerly the Institute of Medicine).

The guideline-recommended antenatal care services should be received at the appropriate gestational age during the pregnancy. The gestational age at the time of the test will be calculated as the date of the test minus the approximate date of last menstrual period (in days). We will approximate the enrollee's date of last menstrual period using the child's date of birth and obstetrician's estimate of gestational age at delivery from the vital records. If these fields are missing, we will define the approximate date of last menstrual period as the beginning date of the index pregnancy (defined above).

Each of these outcomes can only be measured among pregnancies that reach the gestational age at which the care is recommended. The main analyses will only include pregnancies that last at least as long as the gestational age recommended for each outcome. However, it is possible that NFP has a direct effect on gestational age, which would mean that the sample of mothers observed could differ across treatment and control arms. If that is the case (i.e., if gestational age at birth between treatment and control group is statistically significantly different), then we will conduct a bounding exercise as a robustness check for the guideline-concordant care outcomes. Using Group B Strep as an example, the main analysis will compute the average treatment effect (ATE) among people whose pregnancies last at least 35 weeks. If gestational age is statistically significantly different between control and treatment arms, we will estimate two bounds on this ATE: (1) a recalculated ATE assuming *all* people who

did not reach 35 weeks' gestation would have received the test, and (2) a recalculated ATE assuming *none* of the people who did not reach 35 weeks' gestation would have received the test.

Table 1.3. Codes for analyses of antenatal care utilization and quality

	CPT/HCPCS	NDC	ICD-10

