In our clinical trials registry, we defined a measure of mental health treatment follow-up care as: a second antidepressant prescription or outpatient mental health visit within 120 days of the initial treatment ("acute phase"). However, as noted above, differential Medicaid coverage rates between the treatment arms after 60 days postpartum may preclude us from measuring the treatment effect for this outcome reliably. For example, if treatment group members are more likely to be enrolled in Medicaid after 60 days postpartum than control group members, observed differences in mental health treatment patterns between the treatment and control groups could be due to group differences in the composition of who remains on Medicaid.

To assess whether attrition from full-coverage Medicaid plans affects the comparability of the treatment and control groups, we will assess overall attrition and differences in attrition between the treatment and control groups at the following time points: 60 days (for our main outpatient mental health treatment outcomes), 6 months, 12 months and 24 months postpartum (for other potential measurement periods of interest). We do not consider enrollment in partial-coverage Medicaid plans (such as Family Planning) since these plans cover mental health screenings, but do not reimburse for medications or psychotherapy. Specifically, we will compare partial and continuous enrollment rates in full coverage plans between treatment and control groups at each time point. Continuous coverage will be measured using Medicaid enrollment data and will be defined as enrollment during all months, starting with the month of childbirth through 60 days, 6 months, 12 months and 24 months postpartum. It's possible that while average Medicaid enrollment will not differ between the two groups, the type of women retaining coverage could be affected by NFP. Therefore, we will also test whether the treatment and control group members who remain in the analytic sample at each time point are similar on important baseline characteristics using a joint F-test.

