**Table 4. Prenatal outcomes**

	Primary/secondary	Desired direction (increase or decrease)
At least adequate prenatal care	secondary	increase
Anatomy scan ultrasound (18-22w)	secondary	increase
Dental visit during pregnancy	secondary	increase
Recommended gestational weight gain	exploratory	increase
Number of prenatal visits	exploratory	increase
Number of prenatal ultrasounds	exploratory	increase
Gestational diabetes test (24-28w)	secondary	increase
Tdap vaccination (27-36w)	exploratory	increase
Group B streptococcus test (35-37w)	secondary	increase
Maternal fetal medicine visit	exploratory	increase

Note: Tables 4-10 include all primary, secondary and exploratory outcomes from the published papers resulting from this study, except those where the desired direction of the effect of NFP cannot be determined.

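### The optional comparison of ED use between arms within levels of prenatal care adequacy conditions on an outcome NFP is expected to change, so those contrasts can be biased

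*SAP*

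**What the plan says.** In SAP Addendum 1, under utilization of health care services during pregnancy, the first listed outcome is the "Adequacy of Prenatal Care Utilization Index (APNCU) [vital records data"]. The next is the number of ED visits during pregnancy, from all-payer hospital discharge data. A sub-bullet there says the team may also look at differences between the arms in ED use, split by trimester of the visit and by the enrollee's "overall adequacy of prenatal care (APNCU"). The stated aim is "To better understand the effect of NFP on emergency department utilization".

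Addendum 4, Table 4, lists "At least adequate prenatal care" as a secondary outcome with desired direction increase. The Outcomes section of that addendum explains that these directions show what participation in NFP would be expected to do. For ED use it says the effect could plausibly go either way.

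The SAP recognises the same kind of problem in two other places:

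- **Gestational age** (under Antenatal health). If NFP changes gestational age, "the sample of mothers observed could differ across treatment and control arms". The response is a "bounding exercise as a robustness check for the guideline-concordant care outcomes", to be done if gestational age differs significantly between arms.
- **Medicaid retention** (under Maternal utilization of mental health services). Even if average enrolment is equal, "the type of women retaining coverage could be affected by NFP".

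No caveat, bound or balance check is attached to ED use by APNCU.

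**The concern.** Women join the study before 28 weeks of gestation (Protocol 4.4). An index of care over the whole pregnancy, taken from the birth record, therefore includes care received after assignment. If NFP brings some women up to adequate care, the adequate group in the NFP arm contains women whose counterparts in the control arm sit in the not-adequate group. Within a level, the arms then differ in the kind of woman as well as in the offer of NFP.

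The aim of the split is causal, since it is meant to explain the ED result. The SAP regards either direction of effect on ED use as plausible, so an artefact in either direction would have a ready explanation and could be read as a mechanism.

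**Working it through.** The documents state no adequacy rate, ED rate, effect size or power for this analysis, so there is no figure to reproduce. The check has two parts: whether the conditions for bias are present in the plan, and how large the bias could be under stated assumptions.

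**Conditions.** APNCU is a post-randomisation outcome (Addendum 1), NFP is expected to increase it (Addendum 4, Table 4), and the SAP's bounds cover only the guideline-concordant care outcomes. The first condition for bias, movement between levels, is therefore what the plan expects. The second, that the women moved differ in ED use from the groups they leave and join, cannot be checked from the documents.

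**Formula.** Collapse APNCU to adequate versus not, assume NFP moves women only upward, and assume it changes no woman's ED visits. Let p0 be the control share with adequate care and d the share adequate only because of NFP. Let mA, mC and mN be the mean visits of women who are always adequate, adequate only with NFP, and never adequate.

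- False contrast among adequate = d/(p0 + d) × (mC − mA)
- False contrast among not adequate = d/(1 − p0) × (mN − mC)

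Both vanish if d = 0. If mC = mA the first vanishes, and if mC = mN the second does.

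**Illustration (all rates assumed).** Controls: 30% not adequate with mean 2.5 visits, 70% adequate with mean 1.5. NFP moves 5 points of women, with mean 2.0 visits, to adequate care.

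- Not adequate, NFP arm: (30 × 2.5 − 5 × 2.0)/25 = 2.60, against 2.50 in controls: +0.10
- Adequate, NFP arm: (70 × 1.5 + 5 × 2.0)/75 = 1.533, against 1.50 in controls: +0.03
- Overall, controls: 0.30 × 2.5 + 0.70 × 1.5 = 1.80
- Overall, NFP: 0.25 × 2.60 + 0.75 × 1.533 = 1.80

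Both strata show more ED use under NFP, although the overall difference is zero.

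**Range (all rates assumed).** Take mA = 1.0, mC = 1.5, mN = 2.0 and p0 from 0.6 to 0.8. The arm sizes are the index-birth counts in Addendum 4, Table 3 (3295 NFP, 1637 control). Each setting was simulated 2000 times with overdispersed counts (Poisson with a gamma-distributed mean, variance m + m²) and tested at two-sided 0.05, the level in Protocol 5.1.

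| d | False contrast, adequate | False contrast, not adequate | False positives, adequate | False positives, not adequate | False positives, overall |
|---|---|---|---|---|---|
| 0 | 0 | 0 | 4.7–5.2% | 4.8–6.2% | 5.0–5.4% |
| 0.02 | +0.012 to +0.016 | +0.025 to +0.050 | 4.8–6.6% | 5.0–6.4% | 4.0–5.7% |
| 0.05 | +0.029 to +0.038 | +0.0625 to +0.125 | 10.0–11.0% | 9.0–12.9% | 4.9–5.0% |
| 0.10 | +0.056 to +0.071 | +0.125 to +0.250 | 22.1–26.8% | 21.0–26.4% | 5.3–5.5% |

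The unstratified comparison stays at about its nominal level throughout.

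**The case against.** The strongest reply is that this is an optional look under one secondary outcome. The wording is permissive, no model or stratum test is specified, and the listed outcome remains the comparison of ED visits among all women. That stands, and it sets the weight of the point.

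The size is also uncertain and may be small. In the illustration the strata would hold about 824 versus 491 women (0.25 × 3295 and 0.30 × 1637) and 2471 versus 1146 (0.75 × 3295 and 0.70 × 1637). With Poisson variance the standard errors are √(2.60/824 + 2.50/491) ≈ 0.09 and √(1.533/2471 + 1.50/1146) ≈ 0.04. The artefacts are then about 1.1 and 0.8 standard errors, and less with overdispersion. For women who enrol late, much of the pregnancy precedes assignment, which limits movement. This stands as well, although it does not rule movement out.

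The sentence could also mean a cross-classification of all women, since its other half, trimester of visit, divides the visits and not the women. Comparing arms within levels is the more natural reading, but if a cross-classification was meant, the remedy is a clarification.

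A reader might go further and infer that the stratum contrasts are certain to be biased, or that the ED analysis as a whole is compromised. The documents support neither. They give an expected direction for adequacy but no size of movement and no ED means, and nothing here touches the comparison among all women.

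**Conclusion.** The point holds as a minor one. As written, the within-APNCU contrasts are not randomised comparisons and can be biased as estimates of NFP's effect on ED use. The SAP applies this reasoning to gestational age and Medicaid retention but not here. Finding equal adequacy rates in the two arms would not settle the matter, because the kind of woman in each level could still differ, as the SAP itself says of Medicaid enrolment.

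The bias depends on NFP moving women between levels and on those women differing in ED use. Under the assumed rates it runs from nothing (no movement) to a few hundredths of a visit among adequate women and up to a quarter of a visit among the others (10 points moved). These figures, including +0.10 and +0.03, show that the artefact is possible and should not be read as predictions for this trial.

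**What to change.** Replace the APNCU-stratified contrast with joint outcomes: ED use by APNCU category, compared by arm with all index-birth mothers in the denominator. In the illustration, visits per woman randomised and occurring among not-adequate women would be 0.75 in controls (0.30 × 2.5) and 0.65 under NFP (0.25 × 2.60). Among adequate women they would be 1.05 (0.70 × 1.5) and 1.15 (0.75 × 1.533). The differences, −0.10 and +0.10, sum to zero, so the table shows women changing category and no change in total ED use.

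If the split is kept, or has already been run, label it descriptive and non-causal. Addendum 4 (February 2025) describes the trial manuscripts, including prenatal outcomes, as published or forthcoming, and the documents do not show whether the split was done.

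If the question is who responds differently to NFP, stratify on variables from the baseline survey listed in SAP section B.1: any antenatal visit before the survey, weeks to delivery at enrolment, and ER care in the past six months. Assignment cannot alter these, but they address effect modification, which is a different question from whether ED use changes alongside prenatal care.

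The cost is a change of SAP wording and a little more analysis, with no new data. The downside is that the joint outcome does not give a separate effect within each level of care. The split by trimester of visit can stay as it is.
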